**Introduction:**

The optimal method for removal of polyps 6-9 and 10-15 mm in size is not established. In recent years, the use of cold resection techniques (resection without the use of electrocautery) has been demonstrated to be effective and safer than techniques utilizing electrocautery (hot techniques) for diminutive polyps that are 1-5 mm in size. However, the effectiveness of cold techniques for 6-15 mm polyps has been questioned. Recent studies have shown that cold snare endoscopic mucosal resection (EMR) is non-inferior to hot EMR for 6-9 mm polyps . Another trial showed that hot EMR was superior to cold snaring . Cold EMR, or EMR in general, are both more time consuming than non-EMR techniques. EMR refers to a submucosal injection that takes place prior to the removal of a polyp with a snare. In this study, we propose to evaluate four different treatments for polyps (sized 6mm-15mm). The four treatments are cold snaring

without injection, hot snaring without injection, cold EMR, and hot EMR. Previous published failure rates for 6-9 mm polyps are shown in the attached table.

RCTs of hot vs cold snaring – efficacy data					
Author, date	Polyp sizes	Number of polyps	Cold snaring eradication rate	Hot snaring eradication rate	P value
Aslan, 2013 (abstract)	5-10 mm	118	94.87%	94.37%	NS
Papastergiou, 2017	6-10 mm	164	92.8% * EMR	96.3% * EMR	3.5% difference non-inferior
Kawamura, 2017	4-9 mm	796	98.4%	97.2%	NS
Zhang, 2017	6-9	525 (79% adenomas)	91.5%	98.5%* * EMR	0.01 (for adenomas)

## **Methods:**

A member of the research team will approach a potential subject to discuss participation in the study, including background of the proposed study, inclusion and exclusion criteria, benefits and risks of the procedures and follow-up. If this is of interest to the subject, the informed consent form will be discussed and presented. The subject must sign the consent form prior to enrollment.

All of the colonoscopies will be performed by [name] or one of the Sub-Investigators listed above. During the procedure, once a polyp has been identified and its size fits within the range of the target groups (Group 1: 6-9mm or Group 2: 10-15mm), each subject will be randomized to one of the four resection techniques in a 1:1:1:1 ratio using a computer generated randomization sequence. This treatment will be applied to additional polyps found within either of the target groups (correct size ranges) at the discretion of the physician in that patient. The PI has no preference and actively uses all four of the treatments and is expert in all four of the proposed treatments.

Data will be collected by research team members authorized to be on the study. Data that will be assessed from each polyp include its size, a photograph, location of the polyp in the colon, shape (Paris classification), removal time (in seconds) of each polyp resection, prediction of complete resection, prediction of pathology, actual pathology, and efficacy of resection. Efficacy of resection will be assessed by biopsies in four quadrants of the perimeter of the defect and one biopsy from the center of the defect.

Subjects will receive a follow-up phone call 30 ± 7 days after their colonoscopy.

## **Objectives:**

The primary endpoint of the study will be the efficacy of resection. The hypothesis centers on hot EMR as the gold standard, with an estimated effective resection rate of 97% (Table 1). The trial will be powered for non-inferiority, that is, each of the other arms will be non-inferior compared to hot EMR within a  $> 7\%$  margin. Complications will be recorded, but the study will not be powered for complications.

The study will help to establish the optimal resection technique for 6-9 and 10-15 mm polyps. Although previous studies have compared two of the potential resection methods, no previous study has evaluated all four of the resection methods.

## **Criteria:**

### *Inclusion Criteria:*

- Aged 40 years or older
- Ability to provide informed consent

### *Exclusion Criteria:*

- Subjects with a history of inflammatory bowel disease
- Lesions less than 6mm or greater than 15mm in largest dimension

## **Randomization:**

Once a polyp has been identified and its size fits within the range of the target groups (Group 1: 6-9mm or Group 2: 10-15mm), each subject will be randomized in a 1:1:1:1 ratio using a computer generated randomization sequence. Randomization outcomes include: cold snaring without injection, hot snaring without injection, cold EMR, and hot EMR. The randomized treatment will be applied to additional polyps found within either of the target groups (correct size ranges) at the discretion of the physician in that patient.

The randomization list will include 324 treatments. These randomized treatments will be printed and placed into sealed envelopes pertaining to the randomization number and will be opened following confirmation that the patient is eligible. Randomization will occur on a per procedure basis. Not all 324 randomization numbers generated will be used in the study. Instead, enrollment will be competitive and each site will continue to enroll until a total of 264 patients have been randomized study-wide.

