## **Statistical Analysis & Sample Size:**

A sample size of 66 polyps per treatment (264 total subjects) will have 80% power to detect a non-inferiority margin difference of 7% for the cold EMR, hot snare, and cold snare treatments compared to the hot EMR treatment with an alpha of 0.05.

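### Polyp size group is known before allocation and is part of the study question, but neither the list nor the planned comparison uses it: a cheap improvement of moderate weight

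*Combined protocol and SAP*

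**What the plan says.** The Randomization section makes size a condition of allocation: "Once a polyp has been identified and its size fits within the range of the target groups (Group 1: 6-9mm or Group 2: 10-15mm". The envelopes "will be opened following confirmation that the patient is eligible", so the size group is fixed before the arm is revealed. The Methods section gives the same sequence and records the size of every polyp. The Objectives section says the study will help to establish the best technique for both size groups.

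The allocation itself is described once: "each subject will be randomized in a 1:1:1:1 ratio using a computer generated randomization sequence". On the list, the section says only "The randomization list will include 324 treatments" and that enrolment, shared competitively among sites, stops at 264 patients. No strata, blocks or size-specific lists are mentioned.

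The Statistical Analysis & Sample Size section is one sentence. It states that "A sample size of 66 polyps per treatment (264 total subjects) will have 80% power" for a "non-inferiority margin difference of 7" per cent, "for the cold EMR, hot snare, and cold snare treatments compared to the hot EMR treatment with an alpha of 0.05". It names no test, model, covariate or stratified estimate.

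**The concern.** Size is a named baseline factor, measured for every polyp and available before allocation. If 10-15 mm polyps are harder to remove completely, an arm that happens to receive fewer of them looks better for a reason unrelated to technique. As described, nothing keeps the mix similar across arms, and nothing corrects the risk difference when it is not.

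The trial is sensitive to small shifts because, with 66 per arm and failure rates near 3%, one or two failures decide each verdict. Hot EMR is the shared comparator, so an unlucky mix in that arm moves all three comparisons in the same direction.

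**Working it through.** **Inputs from the documents.** 66 per arm; margin 7 points; alpha 0.05, sidedness not stated (Statistical Analysis & Sample Size); 97% success with hot EMR (Objectives).

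**Assumed, because the documents do not say.** 97% in the other arms; one-sided alpha; simple allocation; one index polyp per patient; share of 10-15 mm polyps q = 30% (20-50% also tried); size gap in success g = 0, 2, 5 or 8 points, the same in all arms.

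**1. The plan's own figure.** The test passes when p_T − p_C − 1.645 × SE > −0.07, with SE = sqrt[p_T(1 − p_T)/66 + p_C(1 − p_C)/66]. Exact binomial enumeration with 97% in both arms gives power of 80.2%. In the range 58 to 75 per arm, 66 is the first size to reach 80%, so the plan's figure reproduces. At one-sided 0.025 it would be 67.2%.

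**2. How few failures decide it.** Hot EMR at 64/66:
- Test arm 63/66: difference −1.52 points, SE 3.32 points, lower limit −1.52 − 1.645 × 3.32 = −6.98. Passes.
- Test arm 62/66: difference −3.03 points, SE 3.62 points, lower limit about −8.98. Fails.

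**3. Chance imbalance in size.** SD of the between-arm difference in large-polyp share = sqrt(2 × 0.3 × 0.7/66) = 8.0 points, so the 95% range is about ±15.6 points. A difference of 10 points or more means at least 7 polyps (7/66 = 10.6%). By simulation it occurs in about 22% of single comparisons, and in at least one of the three in about 46% of trials (roughly 35-53% for q from 20% to 50%).

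**4. Shift in the estimate.** Shift = imbalance × g. With g = 5 points, a 97% average requires 0.97 + 0.3 × 0.05 = 98.5% for small polyps and 93.5% for large ones; check: 0.7 × 98.5 + 0.3 × 93.5 = 97.0. The 95% shift is 15.6 × 0.05 = 0.78 points, about 11% of the margin. Over g = 2 to 10 points and q = 20-50%, the 95% shift runs from about 0.3 to 1.7 points.

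**5. Effect on the verdict.** Simulated pass rates of the unadjusted test for truly equal techniques, given an imbalance of 10 points or more (q = 30%):

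| Size gap | Average success | Imbalance favours test arm | Imbalance against test arm |
|---|---|---|---|
| none | 97% | 80% | 80% |
| 2 points | 97% | 82% | 78% |
| 5 points | 97% | 86% | 73-74% |
| 8 points (98.5% v 90.5%) | 96.1% | 82% | 61-62% |

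The last row is a sensitivity case only: 0.7 × 98.5 + 0.3 × 90.5 = 96.1, below the planned 97%, and its overall power is 72%. At a true 7-point loss with a 5-point gap, false non-inferiority is about 11% v 6.5%.

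**6. Price of the remedy when size has no effect** (97% in both groups, q = 30%). Unadjusted test: 80.2%. Mantel-Haenszel risk difference with Sato variance: about 77.5% if only the analysis changes, 78.8% with stratified allocation. The false-pass rate at a true 7-point loss falls from about 8.5% to 7.5% when only the analysis changes. At a 2-point gap, stratified allocation with this test takes power from 80.2% to 79.0%.

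**The case against.** - **Randomization already covers chance imbalance.** This stands. The unadjusted test's error rates average over every imbalance that could be drawn, and the average variance gain from stratifying is only about 1-4%. A reader might infer that the comparisons are biased or the error rate inflated by the single list; the documents do not support that. Only the conditional argument remains.
- **The size effect is assumed.** This also stands. The Introduction's table covers polyps of 4-10 mm, so there is no tabulated rate for 10-15 mm, and the doubt raised there concerns cold techniques at 6-15 mm, not a size gap in every arm. Equally, nothing supports applying one 97% rate to both groups. At a 2-point gap the stratified test passes 77.0% of the time in the adverse draw, slightly less often than the unadjusted test (77.9%).
- **The plan is silent rather than opposed.** True. No analysis is specified, and blocking or division of the list is not ruled out. One cannot infer that the sponsor decided against stratifying. The remedy is the same: state the scheme.
- **The 46% is not a rate of wrong verdicts.** Correct. It is the chance of a 10-point imbalance in at least one of three comparisons; most such imbalances would leave the verdict unchanged.

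**Conclusion.** The point holds as a cheap improvement of moderate weight. Size is known before allocation and belongs to the study question, yet neither the described list nor the statistical section uses it. Under the 97% average that the plan assumes, with 30% large polyps and a 5-point gap, about one comparison in five draws an imbalance of 10 points or more. The chance of passing for an equal technique then differs by about 12 points according to its direction. The spread narrows to about 4 points at a 2-point gap and vanishes without a size effect.

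Two stronger readings should be resisted. The 82% v 61-62% spread belongs to a scenario that departs from the planned 97%, so it should not be the headline. Nor is a stratified test free when size does not matter: it then costs 1.4 points of power with stratified allocation (80.2 − 78.8) or about 2.7 points with the analysis change alone (80.2 − 77.5).

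All these figures rest on the assumed share and gap, simple allocation, a one-sided 0.05 test and an index-polyp analysis.

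**What to change.** **Randomization section.** Stratify the list by the size group of the polyp that triggers randomization, in permuted blocks at 1:1:1:1. Hold two labelled envelope sets at each site, and revise the count of 324 so that each stratum has surplus for an unknown size mix.

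**Statistical Analysis & Sample Size section.** State that the primary analysis uses the index polyp, and pre-specify a size-stratified risk difference for each comparison with hot EMR, against the same margin. This matters because the allocated technique may also be applied to further polyps of either size, and the section speaks of both polyps and subjects. If additional polyps are analysed, use each polyp's own size and allow for clustering within patient.

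If enrolment has started, change the analysis only.

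**Cost.** No extra patients. More envelopes per site and a small risk of drawing from the wrong set. For a Mantel-Haenszel/Sato test, about 1-1.5 points of power with stratified allocation, or 2-3 points if only the analysis changes. The latter is partly offset by a lower false-pass rate (about 7.5% v 8.5%). Stratified allocation followed by the unadjusted test costs no power and is a reasonable minimum.

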## **Statistical Analysis & Sample Size:**

A sample size of 66 polyps per treatment (264 total subjects) will have 80% power to detect a non-inferiority margin difference of 7% for the cold EMR, hot snare, and cold snare treatments compared to the hot EMR treatment with an alpha of 0.05.

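### With 66 polyps per arm and 97% in every arm, 80% power needs a test whose true error is 8.5%; a test that holds 5% gives about 63%, and the plan names no test, sidedness or rate for the three other arms

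*Combined protocol and SAP*

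**What the plan says.** The whole statistical plan is one sentence: "A sample size of 66 polyps per treatment (264 total subjects) will have 80% power to detect a non-inferiority margin difference of 7" per cent, "for the cold EMR, hot snare, and cold snare treatments compared to the hot EMR treatment", at alpha 0.05. There is no separate analysis section.

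The Objectives section supplies the reference rate: "The hypothesis centers on hot EMR as the gold standard, with an estimated effective resection rate of 97" per cent. It also sets the aim: "The trial will be powered for non-inferiority, that is, each of the other arms will be non-inferior compared to hot EMR". There the margin carries a greater-than sign before the 7%; the sample size section has plain 7%.

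The Introduction tabulates earlier trials. Two of its rows include a hot EMR arm: the second (cold EMR 92.8%, hot EMR 96.3%) and the fourth (cold snare 91.5%, hot EMR 98.5%).

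The Randomization section adds: "The randomized treatment will be applied to additional polyps found within either of the target groups", at the physician's discretion. It does not say whether those polyps enter the primary analysis.

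Nowhere do the documents state the test or interval for non-inferiority, whether alpha is one-sided or two-sided, or the true resection rate assumed for the three arms compared with hot EMR.

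**The concern.** Near 97%, with 66 polyps per arm, about two failures are expected in each arm (66 × 0.03 = 1.98). Normal-approximation tests can then miss their nominal error rate badly, and common tests for the same hypothesis can give different answers on the same data. A claim of 80% power at alpha 0.05 therefore means little until the test is named.

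Two things are at stake. If the analysis uses a test that holds its error, the chance of missing true non-inferiority may be well above the 20% implied. If it uses one that does not, a technique truly 7 points worse than hot EMR is accepted more often than 5% of the time. With no test named, the choice can also be made after the data are seen.

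**Working it through.** **Inputs.** From the documents: 66 per arm, margin 0.07, alpha 0.05, 80% power (Statistical Analysis & Sample Size) and 97% for hot EMR (Objectives). Assumed because not stated: 97% in the other arm (the usual equal-rates convention), one analysed polyp per subject, and one-sided alpha unless noted.

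**Step 1: the usual formula.**

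n = (1.645 + 0.842)² × 2 × 0.97 × 0.03 / 0.07² = 73.4, so 74 per arm.

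Power at 66 = Φ(0.07 / √(2 × 0.97 × 0.03 / 66) − 1.645) = 76.2%. With 1.960 in place of 1.645 it is 65.4%. Neither is 80%.

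**Step 2: exact power and error.** Sum the product of the Binomial(66, p_T) and Binomial(66, p_C) probabilities over all 67 × 67 outcomes in which the test claims non-inferiority. Power is at 97% v 97%; type I error is at 90% v 97%, which lies exactly on the margin. One-sided 0.05:

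| Test | Power | Type I error |
|---|---|---|
| Uncorrected z (Wald) | 80.2% | 8.5% |
| Likelihood ratio | 70.8% | 5.6% |
| Agresti-Caffo | 70.8% | 5.6% |
| Score (Farrington-Manning) | 63.3% | 4.9% |
| Newcombe interval | 63.3% | 4.9% |
| Exact unconditional | 59.9% | 3.7% |
| Continuity-corrected z | 59.6% | 3.3% |

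The stated 80% reproduces, but only in the first row. At two-sided 0.05 (critical value 1.960), Wald gives 67.2% and the score test 46.8%.

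**Step 3: is this peculiar to 97%?** Set the other arm 7 points below hot EMR:

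| Hot EMR rate | Wald error | Score error |
|---|---|---|
| 93% | 5.8% | 5.1% |
| 95% | 6.8% | 5.2% |
| 96.3% (Introduction table) | 7.9% | 5.1% |
| 97% | 8.5% | 4.9% |
| 98.5% (Introduction table) | 10.3% | 4.3% |

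Over hot EMR rates of 85% to 100% the score error peaks at 5.17%. Raising its critical value from 1.645 to 1.663 brings the peak to 4.96% and leaves power at 63.2%.

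**Step 4: dependence on the unstated rate.** Hot EMR at 97%, one-sided 0.05:

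| True rate in the other arm | Score power | Wald power |
|---|---|---|
| 93.5% (3.5 points lower, as in the second table row) | 21% | 33% |
| 96.3% | 53% | 70% |
| 97% | 63% | 80% |
| 97.5% | 71% | 87% |
| 98% | 79% | 92% |
| 98.4% | 85% | 95% |

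The score test reaches 80% when the other technique is truly about 98.05%, roughly one point better than hot EMR.

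**Step 5: does the choice change conclusions?** Take 2 failures with hot EMR and 3 with the other technique. The estimated difference plus the margin is 63/66 − 64/66 + 0.07 = 0.0548.

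- Wald: standard error √[(63/66 × 3/66 + 64/66 × 2/66) / 66] = 0.0332; z = 1.652, above 1.645, so non-inferiority is claimed.
- Score: the rates estimated under a 7-point deficit are 91.0% and 98.0%; standard error 0.0391; z = 1.401, so it is not claimed.

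Failures allowed in the other arm for 0, 1, 2, 3 and 4 hot EMR failures are 2, 2, 3, 3, 4 with Wald and 1, 1, 2, 3, 3 with the score test. At 97% v 97% the rules disagree with probability 17.0%. Every disagreement is a Wald claim that the score test does not support.

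**Step 6: size needed.** Score power at 97% v 97% is 78.6% with 98 per arm and 82.2% with 99, the first size at or above 80%.

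**The case against.** The strongest reply is that 80% is not a miscalculation. It reproduces on a plain reading: equal rates, one-sided 0.05, uncorrected z-test. The plan never says that this test will be used for the analysis, so 8.5% describes a possible test. That is fair, and it is why the finding is that the stated power and alpha do not hold together under these assumptions, not that the sponsor has chosen a faulty test.

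Second, the match is sensitive to the rate. The usual formula gives 66.0 per arm if the other arm is at 97.24%, and 66.3 if both arms are at 97.3%. Since 97% is itself an estimate, rounding could explain 66. This stands: how 66 was reached cannot be told from the documents. It also shows that the power claim rests on a rate the plan does not give.

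Third, there are tests between the two extremes. The likelihood ratio and Agresti-Caffo methods give 70.8% power with 5.6% error, so the loss need not be the full drop to 63%. Even so, neither reaches 80%.

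Fourth, extra polyps could add information. As an assumption only, take m analysed polyps per subject and intra-patient correlation 0 to 0.5, with effective n = 66m / (1 + (m − 1) × correlation). For m = 1.25, effective n is 73 to 82 and score power about 67% to 73%. For m = 1.5, it is 79 to 99 and about 72% to 82%. So 63% is firm only for 66 independent polyps per arm. The documents give neither m nor the correlation, and do not say that these polyps count.

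**Conclusion.** The concern holds. With 97% in both arms and 66 independent polyps per arm, no test checked combines 80% power with an error near 5%. The choice is between 80.2% power with 8.5% error at 90% v 97% (uncorrected z) and 63.3% with 4.9% (score), with intermediate methods at 70.8% and 5.6%. The chance of missing true non-inferiority is then about 37% per comparison with the score test, or 24% by the usual formula, instead of 20%.

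The exact power depends on assumptions that the plan leaves open. A better true rate in the other arm, or several analysed polyps per subject, would raise it. Two-sided alpha or a lower true rate would reduce it, and both Introduction rows with a hot EMR arm show the cold technique lower. The missing decision rule does not depend on any of these, and it affects all three primary comparisons. It should be corrected before analysis.

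**What to change.** In Statistical Analysis & Sample Size, name the primary test and the sidedness of alpha, choosing a method that holds its error near 97%. State the assumed true rate in the three other arms and the unit of analysis, including whether additional polyps count. Then give the power that follows. For example:

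> A technique is declared non-inferior if the lower limit of the one-sided 95% Farrington-Manning interval for the complete resection rate, technique minus hot EMR, lies above −7 percentage points. Assuming 97% in both arms and 66 independent polyps per arm, power is about 63% per comparison.

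If two-sided 0.05 is meant, the figure is about 47%. If another rate or several polyps per subject are intended, say so and give the matching power. Write the margin in Objectives as the same 7 points.

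The cost is a text change and no extra patients; the drawback is that the protocol would state power below 80% at equal 97% rates. Keeping 80% with the one-sided score test would take 99 per arm, or 4 × 99 = 396 subjects, 132 more than the planned 264. That is an option for the sponsor and not part of the correction.

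### Does the primary non-inferiority result depend on an unstated choice about non-adenomas and additional polyps?

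*Combined protocol and SAP*

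**What the plan says.** The section Statistical Analysis & Sample Size consists of one sentence. It states "A sample size of 66 polyps per treatment (264 total subjects) will have 80% power", and the test is of each of the other three techniques against hot EMR with alpha 0.05. No analysis set is defined.

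The other relevant places are these:

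- **Randomization.** A patient is randomised once a polyp of qualifying size is seen, so before pathology is known. Recruitment stops by patient count: "each site will continue to enroll until a total of 264 patients have been randomized study-wide". On further polyps: "The randomized treatment will be applied to additional polyps found within either of the target groups", if the endoscopist so chooses.
- **Criteria.** The lesion criterion is size. Histology is not mentioned.
- **Objectives.** The primary endpoint is efficacy of resection, with 97% expected for hot EMR, and "The study will help to establish the optimal resection technique for 6-9 and 10-15 mm polyps".
- **Methods.** The items recorded for each polyp include "prediction of pathology, actual pathology, and efficacy of resection".
- **Introduction, table of trials.** One cited trial of 6-9 mm polyps is listed with "525 (79% adenomas" and a p-value of "0.01 (for adenomas".

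**The concern.** Two choices are not written down.

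The first is histology. Pathology arrives after randomisation and is recorded for every polyp, and a trial in the protocol's own table was summarised by its adenomas. An analyst could keep every polyp or only the adenomas. Enrolment stops at exactly 4 × 66 with no surplus, so an adenoma-only analysis would fall short of 66 per arm and of 80% power.

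The second is multiplicity within patients. The sample size is in polyps and the stopping rule in patients. The two agree only if one polyp per patient is analysed.

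If the set could be settled once results were visible, the more favourable one could be reported. In a non-inferiority trial that raises the chance of accepting a technique that is worse by the full margin.

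**Working it through.** **Inputs.** From the protocol: 66 per arm, 264 in all, margin 0.07, alpha 0.05, hot EMR at 97%. Assumed: equal true rates under the alternative; a 79% adenoma share, from the one cited 6-9 mm trial (range 70-90%); an unpooled Z test, one-sided 0.05, because the protocol names neither test nor sidedness.

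**1. The stated power.** Declare non-inferiority when (p_T − p_R) − 1.645 × √[p_T(1−p_T)/n + p_R(1−p_R)/n] > −0.07, and sum the binomial probabilities over all outcomes. With both rates 0.97, power is 80.2% at n = 66 and 75.7% at n = 65. The stated 80% is reproduced with one polyp per patient and all pathologies kept. The match is modest evidence for this test, since exact power moves in a sawtooth (79.4% at n = 68).

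**2. Adenomas only.** 66 × 0.79 = 52.1. Power is 66.6% at exactly 52 per arm and 69% averaged over chance adenoma counts (67% at a 70% share, 74% at 90%).

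**3. How often the verdicts differ.** Simulation, all rates 0.97, 79% share, one comparison:

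| All polyps | Adenomas only | Share of trials |
|---|---|---|
| succeeds | fails | 13.7% |
| fails | succeeds | 2.1% |
| total | | 15.8% |

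The total is 18.9% at a 70% share and 10.3% at 90%. For at least one of the three comparisons it is 39% (27-46%). Nearly all of it is lost power. Taking whichever set succeeds lifts the success rate only from 80.2% to 80.2 + 2.1 ≈ 82.4% (simulated, unrounded).

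**4. False non-inferiority from choosing the set.** True rates 97% against 90% in every polyp:

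- all polyps, fixed in advance: 8.5%
- adenomas only, fixed in advance: 7.7%
- either may be reported: 11.0% (12.0% at a 70% share, 10.2% at 90%)

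The addition is 11.0 − 8.5 = 2.5 points. With a score test the figures are 4.9% and 6.6%, an addition of 1.7 points. The excess of 8.5% over 5% comes from the Z test and not from the choice of set.

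**5. The cost of fixing all polyps.** Suppose adenomas resect at 97% against 90% and non-adenomas never fail. The overall rates are 1 − 0.03 × 0.79 = 0.9763 and 1 − 0.10 × 0.79 = 0.921. The deficit is 0.07 × 0.79 = 0.055, inside the margin. The all-polyp analysis then declares non-inferiority in 17.0% of trials (22.6% at a 70% share, 11.9% at 90%), against 7.7% for adenomas only.

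**6. Additional polyps.** The protocol gives no expected number. Assuming independent outcomes and a mean of 0.2, 0.5 or 1.0 extra polyps per patient, index-polyp and all-polyp verdicts differ in 9.1%, 13.3% and 16.8% of trials. Power meanwhile rises from about 80% to 82.5%, 88.2% and 94.3%, so this too is largely a difference in sample size. Correlation within patients would reduce the gain.

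**7. What the text supports.** Criteria, randomisation trigger and objective are all framed by size. Polyps per arm times four equals patients. For adenoma-only there is one cell in a background table about another trial, and the recording of actual pathology, which sits beside predicted pathology and is equally explained by checking the predictions.

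**The case for a change.** The strongest case for requiring a change is that a natural reading is not a pre-specified one, and a non-inferiority claim should not rest on inference from eligibility criteria. The statistical sentence is complete as printed, so the rule was not lost to redaction. Both choices are real: pathology will be to hand, and the extra polyps are treated at the endoscopist's option. Under a Newcombe or Farrington-Manning test at a 79% share the disagreement is 18-20%, so it does not depend on the Z test. A few sentences would close the gap without new patients or data.

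Part of this stands. The rule is not written, the arithmetic is right, and the point about additional polyps has the firmer footing in the text.

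It does not carry the conclusion, for two reasons. The 15.8% counts disagreements between a full analysis and one with about a fifth of the sample removed, which is mostly a statement about power. The error that matters, false non-inferiority, moves by about 2 points. And the obvious remedy, naming all polyps as the primary set, is not free: in the dilution scenario its false non-inferiority rate exceeds that of adenomas only by 17.0 − 7.7 = 9.3 points, more than the 2.5 points it removes when the deficit is the same in every polyp. Naming adenomas instead would drop power to about 69%. Statisticians could reasonably prefer either.

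**Conclusion.** The concern identifies missing detail, not an error in a stated rule or figure. Read as written, the plan analyses one polyp per randomised patient, of whatever pathology, and on that reading its 80% power holds. An analyst would reach this set from the size-only eligibility and from 4 × 66 = 264, and would treat an adenoma-only or all-treated-polyps analysis as supplementary.

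If the set were nevertheless chosen after the results, the harm would be about 1.7 to 2.5 points of false non-inferiority per comparison at a 79% adenoma share. Neither candidate set is clearly better: all polyps keeps the power but can dilute a deficit confined to adenomas, and adenomas only avoids dilution at a cost of about 11 points of power (80% to 69%).

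These sizes rest on a share taken from one 6-9 mm trial, although this study also enrols 10-15 mm polyps; on a 97% reference rate; and on a test that the protocol does not name. The conclusion does not depend on their exact values. No change to the plan follows.
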